Study weeks 0-2 —Study Drug Titration: Following completion of baseline assessments, participants will be randomized 1:1 to prazosin or placebo. The initial dose will be 1 mg prazosin or placebo capsule taken at bedtime for 2 nights. The first dose of prazosin/placebo will be taken while the participant is in bed for the night to avoid orthostatic syncope, an uncommon but recognized “first dose” effect of prazosin or any alpha-1 antagonist if started at a high dose. The first dose effect is avoidable by starting treatment with a low dose (1 mg before bedtime) and then titrating the dose upward gradually. Such titration avoids excessive blood pressure reduction.

The participant will be asked to call the study team the morning after the first dose to make sure there was no occurrence of postural dizziness. If there have not been any adverse events, the participant will be instructed to increase the dose to 1 mg three times per day (morning, afternoon and bedtime) on the third day. The participant will be given 24-hour contact number in case of adverse events when the dose is increased. However, in our prior study of prazosin in AUD, there has been no problem with this dose increase.

Participants will undergo 2 additional titration visits (weeks 1 and 2). At each titration visit, seated /supine and standing BP and HR will be measured, and presence of side effects and/or adverse events will be assessed. Concomitant medications and health status will be updated. The alcohol use calendar will be administered at every study visit. P

Mid-week titration increases will occur if the participant does not experience any unacceptable side effects. A 24-hour contact number will be provided should any adverse events occur at any time.

A dose increase will occur if the participant does NOT have unacceptable side effects. Clinical judgement may be used to maintain or decrease the dose as necessary. If the participant has intolerable side effects during the titration period, the dose will be reduced to the previous titration step. The dose may be re-challenged if clinically appropriate.

Titration will proceed according to the following schedule:

Study Drug Dose Schedule

		AM	MIDDAY	BEDTIME
Week 0/BL	Days 1-2			1 mg
	Days 3-4	1 mg	1 mg	1 mg
	Days 5-7	2 mg	2 mg	2 mg
Week 1	Days 8-10	2 mg	2 mg	6 mg
	Days 11-14	4 mg	4 mg	6 mg
Week 2	Days 15-21	4 mg	4 mg	8 mg
Week 3	Days 22-end of study	4 mg	6 mg	10 mg

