The titration schedule and target dose were chosen based on clinical experience in treating PTSD with prazosin and on our initial study for AUD in which this titration schedule was well tolerated.¹⁵ Typical, effective, and well-tolerated doses of prazosin in Veterans with PTSD treated at VA Puget Sound range between 5-30 mg/day.⁷⁷ In our prior work with prazosin, study participants have tolerated without difficulty abrupt discontinuation of these doses of prazosin with no need for tapered withdrawal.

Weeks 3-5: If participants delay titration for any reason (e.g., dose maintained and not increased due to temporary AE), the dose may be increased/adjusted through week 5. No dose changes will be allowed after week 5. If titration is required, procedures noted for weeks 1-2 (above) will be followed. If no titration is required, procedures for weeks 6-13 (below) will be followed.

Weeks 6-13: Participants will be asked to return at weeks 6, 7, 8, 9, 11, and 13. At each visit, vital signs, including orthostatic BP and HR, will be measured. Side effects and/or adverse events (if any) will be monitored by open-ended AE reporting and the Adverse Symptom Checklist which includes symptoms which may be attributable to prazosin (e.g., lightheadedness, dizziness on standing, palpitations, drowsiness, headache, nausea, lack of energy, weakness, depressed mood). For vital signs parameters, hypotension will be defined as systolic BP < 90 and clinically meaningful orthostatic hypotension defined as ≥ 20 mmHg drop in systolic BP accompanied by lightheadedness or syncope. If the participant develops an unacceptable adverse effect considered related to study drug, downward dose adjustment will be made.

Concomitant medications and health status will be updated.

The alcohol use calendar will be administered at every study visit. Outcome assessments (CAPS, PCL-M, PHQ-9, PACS, SIP, PSQI) will be administered at weeks 8 and 13.

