Prazosin may cause syncope. In most cases this is believed to be due to excessive postural hypotension although occasionally the syncopal episode has been preceded by severe tachycardia with heart rates of 120-180 beats per minute. Syncopal episodes have usually occurred within 30-90 minutes of the initial dose. The incidence of the syncopal episodes is 1% if the initial dose is 2 mg or more. Clinical trials suggest that syncopal episodes can be minimized by starting with a dose of 1 mg and slowly titrating up to the final dose, as we are doing in this study.

In post-marketing experience, Intraoperative Floppy Iris Syndrome (IFIS) has been observed during cataract surgery in some patients who are taking or have taken alpha-1 blockers. The patient's ophthalmologist should be prepared for possible modifications to the surgical technique to reduce the surgical risk of IFIS. If a patient needs to have cataract surgery, he/she should tell his/her eye surgeon that he/she may have taken prazosin in a research study.

Prazosin should not be taken concurrently with trazodone. Potential participants who are taking trazodone for sleep and who are willing to discontinue will be washed out before starting this study. Care should be taken when alpha-1 blockers are combined with erectile dysfunction medications. We will be following VA pharmacy prescribing guidelines regarding these medications. Erectile dysfunction medications will not be allowed during the titration period. Once stable dose has been reached, participants will be allowed to use ED drugs at half the usual clinical dose.

Participants will be monitored at each visit for adverse events. Any adverse event will be managed by the study team as clinically appropriate. If necessary, a participant will be referred for treatment of an adverse event. Adverse event reporting will begin after the dispensing of the first dose of study drug. All events reported prior to dispensing of the first dose of study drug shall be part of the participant's health history.

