Women of childbearing potential must have a negative urine pregnancy test at screen and within one week of starting study drug. Female participants must agree to abstain from sexual relations that could result in pregnancy or use an effective method of birth control acceptable to both participant and the study clinician during the study in order to be eligible. Women who are nursing will not be eligible for study participation. Any woman who becomes pregnant during the course of the study will be discontinued from the study but will continue with customary AUD treatment or treatment with her DBH provider.

Risks of medication side effects will be minimized by starting at a low dose and titrating up to the maximum dose over a period of weeks, by maintaining frequent contact with study participants, and by performing safety assessments on a regular schedule. As a further precaution, male participants will be advised to sit on the toilet for urination during the first week of dose titration.

Vital signs, including orthostatic BP and HR, will be performed at all in-person study visits. Systolic and diastolic BP and HR will be obtained following at least 10 minutes of seated/supine posture and then repeated following 2 minutes of standing. Occurrence of lightheadedness, dizziness on standing, palpitations, drowsiness, headache, nausea, nasal congestion, peripheral edema, and other adverse effects will be rated by a study clinician. For vital signs parameters, unacceptable side effects will include seated/supine hypotension (seated/supine systolic BP < 90) and clinically meaningful orthostatic hypotension (≥ 20 mmHg drop in systolic BP accompanied by lightheadedness or syncope).

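### Minor safety improvement: the sit-to-urinate advice for men lapses after day 7 at 6 mg/day, while the dose keeps rising to 20 mg/day on day 22 or later

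*Combined protocol and SAP*

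**What the plan says.** Section 14.2 (Measures to Minimize Risks of Harm) limits side effects by "starting at a low dose and titrating up to the maximum dose over a period of weeks", together with frequent contact and regular safety assessments. It then adds a further precaution: "male participants will be advised to sit on the toilet for urination during the first week of dose titration". No other section extends that advice.

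The Study Drug Dose Schedule in section 10.1 starts at 1 mg at bedtime and reaches 20 mg/day from day 22. Titration visits are set at weeks 1 and 2, and some steps fall between visits: "Mid-week titration increases will occur if the participant does not experience any unacceptable side effects". After a step-down, "The dose may be re-challenged if clinically appropriate". For participants whose titration is delayed, "the dose may be increased/adjusted through week 5", and "If titration is required, procedures noted for weeks 1-2 (above) will be followed".

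On timing of risk, section 14.1 states: "Syncopal episodes have usually occurred within 30-90 minutes of the initial dose". The same section lists orthostatic hypotension and syncope among reactions seen in 1-4% of trial patients and dizziness at about 10%, and does not confine any of them to the first dose.

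**The concern.** The precaution and the titration have different lengths. Section 14.2 presents dose escalation as lasting weeks, but this protection against a fall stops after the first of them. Most of the dose is added later, and the largest single-dose step comes on the first day without the advice.

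The stake is patient safety on a small scale. Visits check orthostatic blood pressure and heart rate, but the check made when a step is due reflects the previous dose. The hours and days at home after a new dose are not observed. The next-morning call in section 10.1 applies to the first dose only. The analysis, power and interpretation of the trial are unaffected.

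**Working it through.** **Inputs.** Doses are from the section 10.1 schedule, the advice period from 14.2, the week-5 limit from 10.1 (Weeks 3-5), the stated dose range from 18.2, the number randomized from 11.4 and the share of men from 12.1.

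**Plan's own figure.** The last schedule row sums to 4 + 6 + 10 = 20 mg/day, which matches the top of the 1 mg to 20 mg range in 18.2.

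**Daily totals and steps**

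| From day | AM / midday / bedtime (mg) | Total (mg/day) | Rise (mg/day) | Ratio | Largest single-dose step | Within advice? |
|---|---|---|---|---|---|---|
| 1 | 0 / 0 / 1 | 1 | start | – | – | yes |
| 3 | 1 / 1 / 1 | 3 | +2 | 3.00 | +1 | yes |
| 5 | 2 / 2 / 2 | 6 | +3 | 2.00 | +1 | yes |
| 8 | 2 / 2 / 6 | 10 | +4 | 1.67 | +4 (bedtime) | no |
| 11 | 4 / 4 / 6 | 14 | +4 | 1.40 | +2 | no |
| 15 | 4 / 4 / 8 | 16 | +2 | 1.14 | +2 | no |
| 22 | 4 / 6 / 10 | 20 | +4 | 1.25 | +2 | no |

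**Share added after the advice ends**
- Increases: 2 of 6 are covered and 4 of 6 are not.
- Daily dose: 4 + 4 + 2 + 4 = 14 mg, and 14/20 = 70%.
- Bedtime dose: 10 − 2 = 8 mg, and 8/10 = 80%.
- Day 8: the bedtime dose triples (6/2 = 3), a step of +4 mg. No other single-dose step exceeds +2 mg.

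In relative terms the total daily dose rises most inside the covered week (×3 and ×2). The later ratios run from 1.14 to 1.67.

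**Position of the visits.** By the schedule's numbering, weeks 1, 2 and 3 open on days 8, 15 and 22. The day-8 and day-15 steps therefore appear to coincide with the week 1 and week 2 visits. Day 22 opens week 3, when the same procedures apply if titration is still needed. Only day 11, which doubles the morning and midday doses, falls between visits.

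**Delayed titration.** Week 5 is days 36 to 42. An increase in that week comes 36 − 7 = 29 to 42 − 7 = 35 days after the advice ends.

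**Length of an extended precaution, with a one-week tail**
- Planned schedule: the last increase is on day 22, so the tail is days 22-28, giving 28 − 7 = 21 extra days.
- Latest case: an increase on day 42 gives a tail to day 48, so 48 − 7 = 41 extra days.
- Men affected, both arms: 200 × 0.9 = 180.

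**What cannot be computed.** The only syncope figure linked to a dose step is 1% when the initial dose is 2 mg or more (14.1). There is no rate for later steps or for urination, so preventable events cannot be estimated.

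**The case against.** The strongest objection is that the one-week limit fits the risk the protocol describes. Section 10.1 treats orthostatic syncope as an uncommon first-dose effect that a low start and gradual titration avoid. Section 14.1 places most episodes within 30 to 90 minutes of the initial dose. Seven days goes well beyond that, and the covered week has the largest relative rises in daily dose. Section 10.1 also reports that this titration schedule was well tolerated in the earlier alcohol-use study.

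Other protections continue: orthostatic measurements at in-person visits, increases only without unacceptable side effects, step-down, a 24-hour number and an on-call clinician. Each new dose is also checked at the next visit. The documents never explain how sitting helps, and nothing in them supports a one-week tail specifically.

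Much of this stands. It explains why the advice begins in week 1, and it means that no hazard is left without cover. It does not explain why the advice stops just before the largest single-dose step. The sponsor already carries it past the first dose, through the day-3 and day-5 increases. Section 14.1 says syncope usually follows the initial dose, not that it only does so, and section 10.1 still monitors orthostatic hypotension in weeks 6 to 13. The continuing safeguards mostly act once a symptom has occurred or been reported, whereas sitting is meant to act before a fall.

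**Conclusion.** The point holds as an optional, low-cost improvement. It is neither an error nor a contradiction. The advice covers doses up to 6 mg/day and lapses before 4 of 6 increases and 70% of the final daily dose. The milligram shares describe how much escalation lies outside the advice. They do not measure risk.

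The conclusion rests on three assumptions: titration runs to schedule (a participant who is behind at day 7 has even more of the rise uncovered), visits fall at the start of each numbered week, and the advice is meant to prevent falls from postural hypotension. The last is the natural reading, but the protocol does not state it. The benefit is plausible, probably small and not quantifiable from the documents.

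**What to change.** In section 14.2, replace the one-week limit with: *throughout dose titration, until one week after the last dose increase (including increases delayed up to week 5)*. The one-week tail is a judgement, and a shorter one would still be an improvement. If participant-facing text repeats the one-week limit, change it there too.

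The cost is one sentence. The downside is minor inconvenience for about 180 men across both arms: 21 more days on the planned schedule and at most 41 for those whose titration is delayed. The documents do not assess how acceptable this would be or how well men would follow it.

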A blood sample (approx. 10 ml) will be collected at the weeks 8 and 13 for measurement of biological markers of alcohol use (PEth and GGT). GGT measurements will be performed by a Madigan laboratory and results will be placed in the participant's AHLTA record. GGT results will be reported to the participant as clinically indicated and the participant will be referred for medical follow-up, if clinically indicated. PEth samples will be shipped for analysis; however, results will not be available in real time. These results will not be reported to the study participant or to any person not involved in the research.

Study drug adherence will be tracked by pill counts at each study visit.

The blind will be broken at the end of the week 13 visit. Procedures for breaking the blind are described in detail below.

Week 19—6-week follow-up: On week 19 (6 weeks after completion of the week 13 visit), participants will be asked to return for a follow-up visit. At this visit, all outcome assessments (CAPS, alcohol use calendar, PACS, SIP, PSQI, PCL-M, and PHQ-9) will be administered. A blood sample (approx. 10 ml) will be collected for PEth and GGT measurement. Participants will receive a certificate of appreciation at this visit or at the early discontinuation visit as appropriate.

Study personnel will have access to participants' medical records during the period of study participation and for 30 days after study completion or early discontinuation. Records will be reviewed to monitor for changes in health, adverse events, any laboratory results, and completion status of the treatment program. Laboratory results may include urine toxicology screens performed as part of the participant's treatment. Other than the labs listed as being done at screening visit and the GGT that will be obtained at baseline and weeks 8, 13, and 19, no clinical labs will be done as part of the study.

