11.0 Statistical/Data Analysis Plan

11.1 Statistical Considerations:

List the statistical methods to be used to address the primary and secondary objectives, specific aims, and/or research hypotheses. Explain how missing data and outliers will be handled in the analysis. The analysis plan should be consistent with the study objectives. Include any sub-group analyses (e.g., gender or age group). Specify statistical methods and variables for each analysis. Describe how confounding variables will be controlled in the data analysis

Primary Outcome Measures: Analysis of the primary outcomes will follow the ITT principal. For each of the two outcomes, a linear regression model with covariates that include treatment group, the stratifying variables, and baseline value of the outcome will be used to compare the prazosin and placebo groups at 13 weeks. In addition, we will conduct a repeated measures analysis using data from the two points of follow-up (8 and 13 weeks). The repeated measure analysis will be conducted by comparing response profiles between prazosin and placebo groups. An initial comparison will be conducted using the general estimating equations (GEE) method of Liang and Zeger,⁹¹ which allows all observed data points for each participant. Secondarily, an analysis of covariance (ANCOVA) rate of change analysis will be done as a confirmatory or sensitivity analysis. Stratifying variables will be included as covariates in each model since they are factors in the stratification. It is anticipated that a retrieved dropout strategy will

result in a limited number of missing observations. For the GEE analysis no imputation strategy is required. For the ANCOVA analysis the missing data patterns will be evaluated between the treatment groups. If the patterns are similar and the magnitude of missing data is small, a conventional last observation carried forward (LOCF) imputation will be performed. If the amount of missing data is substantial and/or the patterns of missingness disparate, as an alternative to the traditional ANCOVA, the summary statistic method of Dawson⁹² will be employed. This method has been shown to be robust to non-ignorable missingness. The approach summarizes the response profile using a least square slope, and stratifies on the missing data pattern. We will also run analyses to assess the interactions between treatment group and gender.

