We used these preliminary data to power for both the primary outcome measures, the alcohol use calendar (similar to the Time Line Followback from [name] Voice Response [IVR] Standard Drink Units [SDU] data) and the PACS (from [name] data). Using the SDU data gives us 97% power, 2-tailed at $\alpha=0.05$ with a sample size of 60 in each group (total $N=120$). Using the PACS data gives us 76% power, 2 tailed, at $\alpha=0.05$, and 85% power, one tailed, at $\alpha=0.5$, with the same sample size. We have conservatively powered because [name] used IVR methodology and data were from persons with AUD without PTSD, and [name] were from Service Members with PTSD without diagnosed AUD, to power adequately for not only Hypothesis 1 for prazosin efficacy for AUD, but also Hypothesis 2 to determine the effects of PTSD diagnosis on response to prazosin for treatment of AUD.

Assuming an approximately 40% dropout rate, we will randomize 200 participants to have 120 study completers.

11.3 Total number of subjects requested (including records and specimens):

300

11.4 If you are recruiting by study arm, please identify the arms of the study and how many subjects will be enrolled in each arm

randomize 200 on a 1:1 ratio prazosin or placebo

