Describe the plan to address incidental findings and unexpected findings about individuals from screening to the end of the subject's participation in the research. In cases where the subject could possibly benefit medically or otherwise from the information, state whether or not the results of screening, research participation, research tests, etc., will be shared with subjects or their primary care provider. State whether the researcher is obligated or mandated to report results to appropriate military or civilian authorities and explain the potential impact on the subject

It is possible that participants in the prazosin group will experience additional benefit resulting in reduced alcohol use and decreased PTSD symptoms.

Participants will be monitored at each visit for adverse events. Any adverse event will be managed by the study team as clinically appropriate. If necessary, a participant will be referred for treatment of an adverse event.

At the study termination or the week 13 visit, all participants will be offered a follow-up appointment with a DBH provider or clinical health care providers. The blind will be broken at participant termination visit regardless of participant trial completion. (All raters will remain blind and will not be informed of any instances of breaking the blind).

We recognize that not breaking the blind for each participant until all participants have completed the protocol is ideal. However, the appropriate and safe method of initiating open-label prazosin by necessity differs depending on the study drug received in the double-blind study (prazosin or placebo).

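### Early terminators are unblinded at their termination visit, and any self-reported primary outcomes retrieved from them afterwards would enter the 13-week ITT analysis as if blinded

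*Combined protocol and SAP*

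**What the plan says.** **Unblinding.** Section 14.6: "The blind will be broken at participant termination visit regardless of participant trial completion". The reason given is that "the appropriate and safe method of initiating open-label prazosin by necessity differs depending on the study drug received". The same section concedes that holding the blind until all participants finish would be ideal. Its one stated safeguard is that "All raters will remain blind and will not be informed of any instances of breaking the blind". For completers, Section 10.1 gives the order: "The blind will be broken at the end of the week 13 visit".

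**Analysis.** Section 11.1: "Analysis of the primary outcomes will follow the ITT principal". The main model compares the arms at 13 weeks, and a repeated measures analysis adds week 8. On missing data it says: "It is anticipated that a retrieved dropout strategy will" "result in a limited number of missing observations". The retrieval procedure and its timing are not described.

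**Dropout.** Section 11.2: "Assuming an approximately 40% dropout rate", 200 are randomized to obtain 120 completers.

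**Outcomes.** Section 10.2 describes both primary outcomes, the alcohol use calendar and the PACS, as participant self-report.

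**Assessment at early termination.** Section 13.6 calls for the week-13 battery at early termination, but only for participants who cannot tolerate the minimum dose. It does not say whether the battery comes before or after disclosure.

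**The concern.** Three provisions interact. A participant who stops early learns the assignment at the termination visit. The 13-week ITT analysis is meant to include dropouts through retrieval. The outcomes to be retrieved are the participant's own account of drinking and craving. If retrieval takes place after the termination visit, those accounts come from someone who knows the arm, yet nothing in the analysis plan separates them from blinded data.

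Two distortions could follow. Knowing the arm can change what is reported, and blind raters cannot prevent that because the information originates with the participant. Participants who were on placebo may also have begun open-label prazosin, which changes what the retrieved outcome measures. With dropout assumed at about 40%, the group concerned could be large, and the order of assessment and disclosure is stated only for completers.

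**Working it through.** **1. The plan's dropout figure.** Section 11.2 gives 120 completers and 40% dropout. 120 / (1 − 0.40) = 200, as stated, so 200 − 120 = 80 dropouts are expected.

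**2. Exposed share.** Let r be the fraction of the 80 dropouts who are unblinded at a termination visit and then supply week-13 self-reports. The documents give no value for r. Taking the 120 completers as blinded, the share of observed week-13 self-reports that is unblinded is 80r / (120 + 80r):

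| r (assumed) | Unblinded / observed | Share |
|---|---|---|
| 0, or all data taken before disclosure | 0 / 120 or more | 0% |
| 25% | 20 / 140 | 14% |
| 50% | 40 / 160 | 25% |
| 75% | 60 / 180 | 33% |
| 100% | 80 / 200 | 40% |

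**3. Bias from expectation alone.** Suppose knowing the arm shifts the between-arm difference in reports by s SD among unblinded participants, with these participants split evenly between arms. Bias = share × s. The range s = 0.2 to 0.4 SD is assumed.

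- Share 25%: 0.25 × 0.2 = 0.05 SD to 0.25 × 0.4 = 0.10 SD.
- Share 40%: 0.40 × 0.2 = 0.08 SD to 0.40 × 0.4 = 0.16 SD.

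**4. Type I error per outcome.** With n analysed per arm and no drug effect, the test statistic is centred at δ = bias × √(n/2), and the error is P(|Z + δ| > 1.96).

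- Share 25%, n = 80: δ = 0.05 × √40 = 0.32 gives 6.2%; δ = 0.10 × √40 = 0.63 gives 9.7%.
- Share 40%, n = 100: δ = 0.08 × √50 = 0.57 gives 8.7%; δ = 0.16 × √50 = 1.13 gives 20.5%.

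**5. Comparison with the planned effect.** The PACS data in Section 11.2 show a difference of 2.3 with SDs of 5.8 and 3.3. The root-mean-square SD is √((5.8² + 3.3²)/2) = 4.72, so the standardized effect is 2.3 / 4.72 = 0.49. This reproduces the stated 76% two-tailed power with 60 per arm. Against that effect, a bias of 0.05 to 0.10 SD is about 10 to 20%, and 0.08 to 0.16 SD about 16 to 33%.

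**6. What is not quantified.** Open-label prazosin in former placebo participants would tend to shrink a true difference. The documents give no figure for its uptake, so its size cannot be derived.

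**The case against.** The strongest reply is that no described procedure yields post-unblinding primary data before week 19. Section 13.6 places the week-13 battery at the early termination visit, and Section 10.1 places disclosure at the end of the week-13 visit. Assessing first and disclosing second is then a natural reading, and on it the exposed share is 0%. The concrete retrieval steps in Section 11.1 (telephone, mail, shipped study drug) follow missed visits and concern participants still on blinded drug. This reply stands in part, and it is why 0% belongs in the range. It does not settle the matter: Section 13.6 covers dose intolerance only, Section 14.6 gives no order for early terminators, and the retrieval strategy is undefined. On this reading, too, an early assessment stands in for week 13, which the plan would need to say.

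A reader might infer that 40% of the primary data will be unblinded. The documents do not support that. Section 11.6 defines completion by visit counts as well as week-13 attendance, so a non-completer can reach week 13 still blind. Participants lost without a termination visit are not unblinded there. Eighty of 200 is a ceiling.

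A reader might also infer that the result will be biased toward prazosin. That does not follow either, because expectation and open-label use can pull in opposite directions.

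Existing features help somewhat. The completers analysis in Section 11.1 keeps only those on protocol for the full 13 weeks, but it gives up the randomized comparison. PEth and GGT are objective, but secondary. Finally, the safety reason for disclosure in Section 14.6 is legitimate and is not disputed here.

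**Conclusion.** The point holds as a conditional one. If calendar or PACS data are collected from early terminators after the termination visit, they are unblinded, possibly affected by open-label prazosin, and would be analysed as blinded. Completers' week-13 data are not affected. Week 19 is unblinded for everyone, but it lies outside the primary models.

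The share at risk is between 0% and 40%, with 25% as an intermediate case. The bias and error figures rest on assumed values of r and of the reporting shift and cover the expectation component only. The net direction cannot be determined from the documents. The plan's own expectation of few missing observations despite 40% dropout implies either substantial retrieval or assessment at termination, and it should say which. The change is worth making because it is cheap and removes an avoidable threat to both primary outcomes. Confidence is medium, since the retrieval procedure is not described.

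**What to change.** 1. State that the calendar and PACS are completed before the assignment is revealed at every termination visit, whatever the reason for stopping.
2. Reconcile Sections 10.1, 11.1, 13.6 and 14.6 so that they say when dropouts are retrieved relative to unblinding, and whether termination-visit data stand in for week 13.
3. Record the date of unblinding and the dates of any open-label prazosin for each participant.
4. Prespecify a sensitivity analysis of both primary outcomes that sets post-unblinding self-reports to missing and uses multiple imputation. It should accompany the ITT analysis rather than replace it, because the imputation carries its own assumption about the missing values.
5. Report week 19 as unblinded and descriptive.

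No change is proposed to when participants are told their assignment for clinical reasons. If disclosure has to come first, the later data are kept and flagged by date.

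The cost is reordered steps within a visit, dates added to the case report form, and one further analysis with somewhat lower precision.
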